6.11 Criteria for Patient Removal

Diagnosis of >3 bone and/or soft tissue metastases on entry imaging studies before SBRT/SABR. PSA >50 ng/ml before SABR. Progression as defined in section 9.5.5.

Radium-223 administration may be delayed by no more than four weeks for recovery of adverse events. In case of a treatment delay greater than four weeks, treatment should be discontinued. It is important to note that in general (unless otherwise agreed), in cases where study drug has been ordered, the time window is reduced to -3 days to + 3 days, due to decay. If administration has to be postponed more than 3 days after drug has been ordered, replacement of the drug order is required. Dose reduction for radium-223 will not be permitted and subjects with any toxicity requiring radium-223 dose reduction must discontinue radium-223 treatment.

Any toxicity requiring radium-223 discontinuation will be recorded as an AE in the subject's medical record and on the CRF.

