6.15 Withdrawal from Study

In accordance with the Declaration of Helsinki, patients have the right to withdraw from the study at any time for any reason, without prejudice to their medical care. The investigator also has the right to withdraw patients from the study for any of the following reasons:

- Subject withdraws consent for follow-up.
- Subject is lost to follow-up.
- Study is terminated for any reason.
- Occurrence of AEs, if discontinuation of study medication is considered necessary by the Investigator and/or patient.
- Lack of patient compliance.
- Protocol violation.
- Progressive disease as defined in section 9.5.5.

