9.5.5 Clinical Response Parameters

Progression is a composite endpoint defined from the Prostate Cancer Working Group 2 (PCWG2) criteria for metastatic castrate resistant prostate cancer (mCRPC) (75) and our previous trials in a population of men with biochemical failure without metastases (72-74). Progression will be defined as either: 1) a $\geq 25\%$ increase in PSA from nadir (and by ≥ 2 ng/mL), requiring confirmation ≥ 4 weeks later (PCWG2 criteria); and/or, 2) clinical/radiographic-progression defined as symptomatic progression (worsening disease-related symptoms or new cancer-related complications), or radiologic progression (on CT scan: $\geq 20\%$ enlargement in sum diameter of soft-tissue target lesions [RECIST 1.1 criteria]; on bone scan: ≥ 1 new bone lesions), initiation of ADT or death due to any cause, whichever occurs first. Death is considered a severe adverse event here.

Progression Free Survival (PFS) is defined as the time from starting treatment to the time of progression as defined above. Subjects who do not progress will be censored at the time of the last contact.

ADT Free Survival (ADT-FS) is defined as the time from starting treatment to the time of initiation of palliative ADT. ADT will typically be initiated on tumor progression and/or development of new metastases. Subjects who do not start ADT will be censored at the time of the last contact.

Time to Progression (TTP) is defined as the time from starting treatment to the time of first documented tumor progression or new lesions by CT and/or bone scan or initiation of ADT. Subjects who do not progress will be censored at the time of the last contact. In addition, death from any cause will also be censored.

Time to New Metastasis (TNM) is defined as the time from starting treatment to the time of a new documented tumor metastasis by CT and/or bone scan. Subjects who do not progress will be censored at the time of the last contact.

Overall Survival (OS) is defined as the time from starting treatment until death due to any cause. For subjects who do not die, time to death will be censored at the time of last contact.

Locoregional Control (LRC) is defined as the time from starting treatment until local and/or regional relapse is documented

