14.5 Analysis of Secondary Objectives

- For safety analysis, adverse events will be summarized by type and grade.
- Kaplan-Meier (KM) estimates will be used to summarize ADT-free survival (ADT-FS), time to locoregional progression (TTLP), time to distant progression (TTDP), time to new metastasis (TNM) and duration of response over time. The median PFS, ADT-FS, TTLP, TTDP TNM and duration of response will be reported.
- The efficacy of SABR + Radium-223 in men with oligometastatic disease will also be determined by measuring local control of each lesion at 12-months.

Each metastatic lesion will be considered a target lesion and independently evaluated for response using RECIST 1.1 or bone scan evaluation criteria above. The lesion will be coded as being locally controlled if it is considered stable radiographic disease or if there is evidence of a partial or complete response. Local control assessment will start at three months following randomization and continuous assessment will be pursued during the follow-up period. The proportion of the lesions that have a stable or better response will be estimated using generalized estimating equation.

- Quality of life will be assessed using the Brief Pain Inventory form. An overall score will be calculated pre-treatment and at the time of the 2nd radiologic reassessment. The change in score will be evaluated with a paired t-test.

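### The 12-month local-control proportion has no rule that a lesion failing before month 12 stays a failure, and none for lesions with no month-12 scan or one taken after ADT, so the rate may be overstated

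*Combined protocol and SAP*

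**What the plan says.** Local control at 12 months is a named secondary objective (Synopsis, 3.3, 14.1.2). Section 14.5 says that efficacy "will also be determined by measuring local control of each lesion at 12-months". Each lesion is judged separately by RECIST 1.1 or the bone-scan criteria. On coding: "The lesion will be coded as being locally controlled if it is considered stable radiographic disease", or if it shows a partial or complete response. Assessment begins three months after randomization, and "continuous assessment will be pursued during the follow-up period". The estimator is then given: "The proportion of the lesions that have a stable or better response will be estimated using generalized estimating equation".

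Three other sections bear on who still has a readable lesion at month 12:

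- Section 6.11 lists among the removal criteria: "Progression as defined in section 9.5.5".
- Section 6.15 lists among the reasons for which the investigator may withdraw a patient: "Progressive disease as defined in section 9.5.5".
- Section 9.5.5 states: "ADT will typically be initiated on tumor progression and/or development of new metastases".

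Against these, Section 6.7.2 schedules bone scan and CT/MRI at 6 and 12 months for all patients, and Sections 6.10 and 14.2 set two years of follow-up. Footnotes R and U of the two study calendars limit the day-360 PSMA PET/CT to men still enrolled.

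**The concern.** Section 14.5 does not say which assessments enter the GEE. The sentence on continuous assessment settles when lesions are looked at, not whether a failure at month 6 still counts at month 12. If the analysis uses month-12 status, or pools visits, an early failure can be lost in two ways:

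- **Missing.** The man is removed at progression and has no month-12 scan, so an ordinary GEE uses no month-12 record for that lesion. Unweighted GEE generally needs missingness unrelated to outcome; here it can follow directly from the outcome observed at month 6.
- **Reversed.** The man starts ADT, the lesion shrinks, and month 12 reads as stable or better.

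Both routes push the rate the same way, upward. Pooling the visits would keep the month-6 record but would not estimate a 12-month rate. At stake is the credibility of the reported local-control figure, not the primary PFS result.

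**Working it through.** **1. The plan's own figures.** No rate, precision or sample size is stated for local control. The PFS design (14.2: medians 10 and 20 months, one-sided alpha 0.1, 80% power, 18 + 12 months) does reproduce. Schoenfeld's formula gives 38 events. Exponential event probabilities of 0.751 and 0.509 average 0.630, so N = 38/0.630 = 60.3. Then 60/0.95 = 63.2, which becomes 64 at 32 per arm.

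**2. How many men could have missing or post-ADT status.** With exponential PFS, the share progressed by month t is 1 − 0.5^(t/median).

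- SABR: 1 − 0.5^(12/10) = 56.5%, about 18 of 32. This agrees with the 50–60% quoted in 14.2.
- SABR + Radium-223: 1 − 0.5^(12/20) = 34.0%, about 11 of 32.

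If none of these men had a usable month-12 reading, 43.5% and 66.0% would contribute. With an assumed 90% control among those observed, and patient shares standing in for lesion shares, the extreme bounds are:

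- SABR: 0.435 × 0.90 = 39%, up to 0.392 + 0.565 = 96%.
- SABR + Radium-223: 0.660 × 0.90 = 59%, up to 0.594 + 0.340 = 93%.

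**3. Can a failed lesion read as controlled?** Section 9.5.1 measures progression from the smallest size since treatment began. Take a hypothetical lesion with nadir 10 mm that grows to 14 mm: +40%, a failure. If it then shrinks to 11 mm on ADT it is 10% above nadir, below the 20% threshold, and reads as stable.

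**4. Size of the overstatement.** Let C be true 12-month control, F = 1 − C, and q the share of failures seen before the month-12 scan and then lost. Neither C nor q is in the documents, so both are assumed. If lost failures are dropped and losses for other reasons are unrelated to local status, the reported rate is C/(C + F(1 − q)). If they are re-coded as controlled, it is C + Fq.

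| Assumed C | q | Dropped | Re-coded |
|---|---|---|---|
| 75% | 25% | 80.0% | 81.25% |
| 75% | 50% | 85.7% | 87.5% |
| 75% | 75% | 92.3% | 93.75% |
| 90% | 25% | 92.3% | 92.5% |
| 90% | 50% | 94.7% | 95.0% |
| 90% | 75% | 97.3% | 97.5% |
| 95% | 50% | 97.4% | 97.5% |

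A q near one half is what a constant lesion hazard with one scan at month 6 would give. Control at month 6 is then √C, so the share of failures occurring by month 6 is (1 − √C)/(1 − C) = 1/(1 + √C): 0.536 at C = 75% and 0.513 at C = 90%. Dropping all of them reports C/√C = √C, that is 86.6% and 94.9%. This is arithmetic on an assumption, not evidence from the trial.

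**The case against.** A reader might infer that the plan definitely scores month-12 status alone, that every early local failure leads to removal or ADT, and that the overstatement is therefore certain. The documents do not support that, for these reasons:

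- **Month-12-only scoring is one reading.** Assessment is described as continuous from month 3, and the month-6 records may be meant to enter the analysis.
- **Not every local failure meets 9.5.5.** Soft tissue is judged on the sum of diameters. On bone scan only a new lesion counts, and bone lesions are non-measurable (9.3). Every man has at least one bone metastasis (5.1.1), and worsening of a treated one is not itself a listed imaging event.
- **Loss of the month-12 scan is not certain.** Imaging at 12 months is planned for all patients (6.7.2), 6.15 gives a right rather than a duty to withdraw, and 6.11 does not say that imaging stops.
- **Most progression is expected elsewhere.** Section 4.5 names microscopic sites as the predominant mode after SABR. Many lesions missing at month 12 may be locally controlled, which costs precision without necessarily inflating the rate.
- **Post-progression response is discouraged elsewhere.** Sections 9.5.3 and 9.5.4 end best response and response duration at progression. This wording is at patient level and does not govern lesion coding in 14.5.
- **Time to locoregional progression is already planned** by Kaplan–Meier. It combines local with regional relapse and is to be reported as a median, so it does not replace per-lesion control at 12 months.

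These points limit the claim to possible overstatement of unknown size. None of them supplies the missing rule.

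**Conclusion.** The point holds as an analysis gap with a predictable direction. Where early local failures are dropped or re-coded, the 12-month rate can only be too high. How often that would happen cannot be computed from the documents.

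The illustration of 75% reading as about 86%, and 90% as about 95%, assumes that half of the failures are seen before month 12 and that all of those are dropped. It sits toward the upper end of what is plausible, because not every early failure would be lost. At an assumed 95% control the same assumption moves the rate by only about 2.4 points. The figure of more than 75% in Section 4.2 concerns spine, lung and liver metastases generally and does not fix the rate for this trial.

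The unequal progression shares (56.5% and 34.0%) might suggest that the comparison of arms is biased. That is not shown: if C and q are the same in both arms, both rates are inflated equally. What the shares do show is that missing or post-ADT status could be substantial and unequal, which is reason enough to fix the rule before the data are seen. The endpoint is secondary and unpowered, so this should be changed but does not threaten the primary analysis.

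**What to change.** In Section 14.5:

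1. Define a lesion as a local failure at 12 months if it met the local-failure criterion at any assessment up to and including month 12. Later shrinkage, including on ADT, does not reverse it.
2. Estimate the 12-month cumulative incidence of first local failure per lesion, by arm, with death as a competing event and variance clustered by patient. Censor failure-free lesions at their last evaluable scan. Read the estimate at the close of the Day 361 visit window (+7 days), so that failures found on that scan are counted.
3. Give censoring at ADT start only as a sensitivity analysis. ADT typically follows progression, so that censoring may be informative.
4. If GEE is kept, use the ever-failed indicator and keep the failed lesions of removed men in the denominator. State a rule for lesions lost failure-free before month 12 (for example inverse-probability-of-censoring weights). Keeping every failure while dropping those lesions would bias the rate downward.
5. Report, by arm, the number of lesions without a month-12 scan and the number scanned after ADT.

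Sections 6.11 and 6.15 (removal or withdrawal at progression) and Section 6.7.2 (12-month imaging for all patients) must be reconciled, so that it is clear whether lesion imaging continues after progression.

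The cost is SAP wording and one clustered cumulative-incidence analysis on data already being collected. The sample size stays at 64. The reported local-control rate may be less favourable.

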5.1 Inclusion Criteria

- 5.1.1 Patient must have at least one and up to three asymptomatic metastatic tumor(s) of the bone or soft tissue (with at least one bone metastasis) within the past 3-months that are ≤ 5.0 cm or <250 cm 3 as seen on either CT/MRI scan and/or bone scan. Up to five lesions are allowed on advanced functional imaging such as fluciclovine (Axumin), choline or ^{18}F -DCFPyL (“PyL”) PET-CT scan within the past 6-months. (PET-CT scan is reasonable for study entry imaging as an alternative to CT/MRI scan and/or bone scan)
- 5.1.2 Patient must have had their primary tumor treated with surgery and/or radiation.
- 5.1.3 Histologic confirmation of malignancy (primary or metastatic tumor).
- 5.1.4 PSADT <15 months. PSA doubling time (PSADT) will be calculated using as many PSA values that are available from time of relapse (PSA > 0.2). To calculate PSADT, the Memorial Sloan Kettering Cancer Center Prostate Cancer Prediction Tool will be used. It can be found at the following web site: <https://www.mskcc.org/homograms/prostate/psa-doubling-time>.
- 5.1.5 Patient may have had prior systemic therapy and/or ADT associated with treatment of their primary prostate cancer. Patient may have had ADT

associated with salvage radiation therapy (to the primary prostate cancer or pelvis is allowed).

5.1.6 PSA ≥ 0.5 but ≤ 50 .

5.1.7 Any testosterone lab within the past 6 months $> 50\text{ng/dL}$.

5.1.8 Patient must be ≥ 18 years of age.

5.1.9 Patient must have a life expectancy ≥ 12 months.

5.1.10 Patient must have an ECOG performance status ≤ 2 .

5.1.11 Patient must have normal organ and marrow function as defined as:

Before the first administration of Xofigo, the absolute neutrophil count (ANC) should be $\geq 1.5 \times 10^9/\text{L}$, the platelet count $\geq 100 \times 10^9/\text{L}$ and hemoglobin $\geq 10 \text{ g/dL}$.

5.1.12 Patient must have the ability to understand and the willingness to sign a written informed consent document.

5.1.13 LDH lab performed within 6 months of enrollment.

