Q.	After randomization, only interval concomitant medications, interval medical history, and limited physical exam information needs to be collected. This only needs to occur once, either on Day 1 visit or during SABR treatment.
R.	Per SOC, patient's will have a PSMA PET/CT prior to enrollment/randomization. Patients who are still enrolled in the trial will have a PSMA PET/CT 360 Days from initial PSMA PET/CT (see S).
S.	ONLY for sites participating in PSMA PET-CT: If applicable, patient's will have a PSMA PET/CT 12 Months from the second completed PSMA PET (~approximately 13/14 months from randomization)
T.	Additional follow-up visits are for 1 year. Follow up after 12 months will be conducted Q6 months, as SOC (months 18 and 24).
U.	All AEs will be collected using CTCAE version 4.0. All skeletal related events will need to be collected throughout the trial and during the follow-up period.
V.	If Pre-study and Day 1 occurs within 2 weeks of each other, the following labs do not need to be repeated for Day 1: PSA, LDH, Testosterone, CBC w/Diff, and CMP. If PSA is completed within 2 weeks from Day 1, regardless of Footnote D, then it may be used. If PSA has been drawn greater than 2 weeks from Day 1, then it must be repeated. Research Blood for Day 1 MUST be completed PRIOR to SABR and/or Xofigo (Radium-223) injection.
W.	During 18 and 24 month follow-up: limited physical exam, ECOG (performance status) changes to conmedications, changes to medical history, Adverse Events, BPI (QoL), and PSA are required for documentation (Epic Note). Any additional labs or imaging are at the discretion of the treating physician.

STUDY CALENDAR: SBRT + Xofigo ARM

	Pre-Study ^Y	Day 1 ^Y	Day 15	Day 29	Day 43	Day 57	Day 61	Day 71	Day 85	Day 31 (+/- 7 days)	Day 39	Day 113	Day 127	Day 141	Day 155	Day 181 (+/- 7 days)	Day 361 (+/- 7 days)	Follow-up Q6 Month ^W (+/- 7 days)
ICF	X																	
Demographics	X																	
Medical History	X									X ^T						X ^T	X ^T	X ^Z
Concomitant Medications	X									X ^T						X ^T	X ^T	X ^Z
Physical Exam	X									X ^T						X ^T	X ^T	X ^Z
Performance Status	X									X ^F						X	X	X ^Z
Vital Signs	X									X								
Height	X									X								
Weight	X									X								
CBC w/ Diff ^A	X ^C									X ^I						X	X	X ^Z
LDH	X ^C									X ^I						X	X	X ^Z
Serum Chemistry ^B	X ^C									X ^I						X	X	X ^Z
Testosterone	X ^C									X ^I						X	X	X ^Z
PSA	X ^D									X ^I						X	X	X ^Z
Bone Scan	X ^E									X ^I						X	X	X ^Z

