9. MEASUREMENT OF EFFECT

9.1 Antitumor Effect – Metastatic Tumors

For the purposes of this study, patients should be re-evaluated for radiographic response 6- and 12-months after randomization. Trial radiologists evaluating for treatment responses will be blinded to the treatment group and treatment specifics (lesions treated with SABR).

Response and progression will be evaluated in three ways:

- 1) Using Response Evaluation Criteria in Solid Tumors (RECIST 1.1) Committee definition. Changes in only the largest diameter (uni-dimensional measurement) of the tumor lesions are used in the RECIST criteria.
- 2) Lesions by bone scan will be evaluated as positive, negative or no change. MRI of the bone lesion can be used to clarify equivocal lesions.
- 3) Serial PSA changes.

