14.1.2 Secondary Objectives

- To describe the toxicity of SABR and SABR + Radium-223 delivered for the population enrolled using grading with CTCAE v. 4.0
- To determine local control at 12-months after SABR and SABR + Radium-223 in patients with oligometastatic disease.

- To assess time to locoregional progression, time to distant progression, time to new metastasis and duration of response after randomization to SABR *versus* SABR + Radium-223.
- To assess ADT-free survival (ADT-FS) of this patient population after randomization defined as the time interval between the day of randomization and the initiation of ADT. ADT will typically be initiated on progression and/or development of new metastases.
- To assess quality of life following SABR *versus* SABR + Radium-223 arms. Brief Pain Inventory form which will be filled out by the patient at the treatment response intervals outlined above.

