APPENDIX I: Brief Pain Inventory Form

STUDY ID# _____	HOSPITAL # _____									
DO NOT WRITE ABOVE THIS LINE										
Brief Pain Inventory (Short Form)										
Date: _____ / _____ / _____	Time: _____									
Name: _____	Last	First	Middle Initial							
1. Throughout our lives, most of us have had pain from time to time (such as minor headaches, sprains, and toothaches). Have you had pain other than these everyday kinds of pain today?										
1. Yes		2. No								
2. On the diagram, shade in the areas where you feel pain. Put an X on the area that hurts the most.										
3. Please rate your pain by circling the one number that best describes your pain at its worst in the last 24 hours.										
0 No Pain	1	2	3	4	5	6	7	8	9	10 Pain as bad as you can imagine
4. Please rate your pain by circling the one number that best describes your pain at its least in the last 24 hours.										
0 No Pain	1	2	3	4	5	6	7	8	9	10 Pain as bad as you can imagine
5. Please rate your pain by circling the one number that best describes your pain on the average.										
0 No Pain	1	2	3	4	5	6	7	8	9	10 Pain as bad as you can imagine
6. Please rate your pain by circling the one number that tells how much pain you have right now.										
0 No Pain	1	2	3	4	5	6	7	8	9	10 Pain as bad as you can imagine

7. What treatments or medications are you receiving for your pain?

8. In the last 24 hours, how much relief have pain treatments or medications provided? Please circle the one percentage that most shows how much relief you have received.

0% 10% 20% 30% 40% 50% 60% 70% 80% 90% 100%
No Relief Complete Relief

9. Circle the one number that describes how, during the past 24 hours, pain has interfered with your:

A. General Activity

0 1 2 3 4 5 6 7 8 9 10
Does not Interfere Completely Interferes

B. Mood

0 1 2 3 4 5 6 7 8 9 10
Does not Interfere Completely Interferes

C. Walking Ability

0 1 2 3 4 5 6 7 8 9 10
Does not Interfere Completely Interferes

D. Normal Work (includes both work outside the home and housework)

0 1 2 3 4 5 6 7 8 9 10
Does not Interfere Completely Interferes

E. Relations with other people

0 1 2 3 4 5 6 7 8 9 10
Does not Interfere Completely Interferes

F. Sleep

0 1 2 3 4 5 6 7 8 9 10
Does not Interfere Completely Interferes

G. Enjoyment of life

0 1 2 3 4 5 6 7 8 9 10
Does not Interfere Completely Interferes

Copyright 1991 [name]
Pain Research Group
All rights reserved.
Used by permission.

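### The quality-of-life analysis in Section 14.5 tests within-patient change in an undefined overall BPI score, so it cannot answer the between-arm objective in Section 14.1.2, and it leaves scheduled BPI forms unused

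*Combined protocol and SAP*

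**What the plan says.** **Objective.** Section 14.1.2 states it as a contrast between arms: "To assess quality of life following SABR *versus* SABR + Radium-223 arms". The synopsis does the same.

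**Analysis.** Section 14.5 gives the whole plan in two sentences: "An overall score will be calculated pre-treatment and at the time of the 2nd radiologic reassessment", then "The change in score will be evaluated with a paired t-test". It does not say which items form the score, how they are scaled, whether the test is run by arm or pooled, or what happens when a form is missing.

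**Timing.** Section 9.1 says "patients should be re-evaluated for radiographic response 6- and 12-months after randomization", and Section 6.7.2 schedules imaging at the same months. The second reassessment is therefore month 12.

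**Collection.** Section 14.1.2 has the patient complete the form at the response assessments, so at month 6 as well as month 12. For the 18- and 24-month visits, footnote W of the SABR-only calendar and footnote Z of the combination calendar both say "Adverse Events, BPI (QoL), and PSA are required for documentation".

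**Form.** Appendix I has four 0-10 severity items (3 to 6), for example "Please rate your pain by circling the one number that best describes your pain at its worst in the last 24 hours", and seven 0-10 interference items (9A to 9G). High is bad on all eleven. Item 8 asks "In the last 24 hours, how much relief have pain treatments or medications provided" and is answered from 0% to 100%, where high is good. No scoring rule is given.

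**Progression.** Section 6.11 lists progression among the criteria for patient removal, and Section 6.15 lets the investigator withdraw a man for it. Sections 6.10 and 14.2 follow patients for two years and make no exception for progression.

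**The concern.** The endpoint and the test do not match the question. A paired t-test asks whether scores changed from baseline in the men tested. Run separately by arm, it gives two p-values whose comparison is not a test of the difference between arms. Run on both arms pooled, it removes the treatment contrast altogether. Either way the trial could finish without a prespecified estimate of what radium-223 adds to, or takes from, patient-reported pain.

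Because the score is undefined, the analyst must choose it later, possibly with the data in view. Severity only, interference only, an average and a raw total can give different answers.

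Only one post-baseline time point is used. By then many men will have progressed, more of them in the SABR arm if the design hypothesis is right. A complete-pairs test has no means of handling unequal loss, while forms scheduled at other visits go unused.

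**Working it through.** **1. Objective against test.** The objective is a difference between two randomized arms. The planned statistic is the mean of (month 12 minus baseline) within patients, tested against zero. No term for arm appears, so the stated analysis does not estimate the stated objective.

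**2. Visits scheduled against visits analysed.** BPI is due at baseline, months 6 and 12 (Section 14.1.2 with Section 9.1) and months 18 and 24 (calendar footnotes). Section 14.5 uses baseline and month 12, which is one of four post-baseline visits.

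**3. What a raw total would contain.** This step is conditional, because the plan does not define the score.
- Severity, items 3 to 6: 4 × 10 = 40 points, high is bad.
- Interference, items 9A to 9G: 7 × 10 = 70 points, high is bad.
- Relief, item 8: 100 points, high is good.
- Total: 40 + 70 + 100 = 210. Relief share: 100/210 = 47.6%.

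As an illustration, take a man with all eleven items at 2 and relief 0%. His raw total is 22 + 0 = 22. Later all eleven items are at 1 and relief is 50%, so the total is 11 + 50 = 61. Every pain item improved, yet the total rose by 39. Without item 8 it falls from 22 to 11.

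**4. Progression by month 12.** The inputs come from Section 14.2: median PFS 10 and 20 months, hazard ratio 0.5, one-sided alpha 0.1, 80% power, 18 months of accrual plus 12 of follow-up, 30 per arm, and 32 per arm after 5% drop-out.

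The plan's own figure comes first. Events needed (Schoenfeld) = (1.2816 + 0.8416)² / (0.25 × (ln 0.5)²) = 4.508/0.1201 = 37.5, so 38. With exponential PFS and uniform accrual, the event probability is 1 − (e^(−12λ) − e^(−30λ))/(18λ), where λ = ln 2/median. This is 0.751 for a median of 10 and 0.509 for 20. Expected events are 30 × (0.751 + 0.509) = 37.8, which gives 80.2% power. Then 60/0.95 = 63.2, or 64 in two equal arms. The design reproduces, so its medians can be carried forward.

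Proportion progressed by month t = 1 − 0.5^(t/median):

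| Month | SABR | SABR + radium-223 | Progression-free of 32 |
|---|---|---|---|
| 6 | 34.0% | 18.8% | 21.1 and 26.0 |
| 12 | 56.5% | 34.0% | 13.9 and 21.1 |

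The SABR figure agrees with the plan's statement that at least 50-60% progress within 12 months.

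**5. From progression to missing forms.** No retention rate after progression is given, so only a range can be shown, counting loss through progression alone.
- If no progressor leaves, 32 and 32 pairs remain.
- If only men who progressed by month 6 are missing, about 21 and 26 remain.
- If every man who progressed by month 12 is missing, about 14 and 21 remain.

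**The case against.** Several counter-arguments have force.

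- **Item 8 may never enter the score.** Nothing in Section 14.5 says that items are summed raw or that relief is counted. A reader might infer that the total is dominated by item 8, or that the reported change will have the wrong sign. The documents do not support that. What they support is that the score is undefined and that one construction left open would behave badly.
- **Progression is not a missing form.** A reader might take 14 and 21 of 32 as the forms available. They are progression-free counts. Section 14.2 keeps men for two years, the 18- and 24-month BPI is required without exception for progression, and Section 6.15 permits withdrawal but does not require it. Scheduled PSA is at months 3, 6 and 12 and imaging at 6 and 12, so progression between months 6 and 12 may be found at the month-12 visit, when the form is due.
- **There is no planned between-arm comparison to bias.** A reader might say that the dropout pattern biases the treatment comparison toward no difference. The plan makes no such comparison for quality of life, and whether men who progress have more pain is not stated.
- **Baseline scores are not known to be near zero.** Eligibility requires "at least one and up to three asymptomatic metastatic tumor(s", but the BPI severity items are not limited to cancer pain and no baseline data are given.
- **Section 3.3 words the objective for the combination arm only.** A within-arm test would fit that wording. The synopsis and Section 14.1.2, the statistical section, both state the contrast.
- **The SABR-only calendar's BPI row is unreadable in the extracted text.** Month-6 collection in that arm therefore rests on Section 14.1.2.

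The first four points limit how far the concern can be taken. None of the six supplies a definition of the score, an analysis between arms, or a use for the other visits.

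**Conclusion.** The point holds in this form. The planned test cannot answer the quality-of-life objective in Section 14.1.2, the score it uses is undefined, and it uses one of four scheduled post-baseline visits. These three findings rest on the text alone.

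Two further statements are conditional. If a raw total included item 8, that item would supply 100 of 210 points in the reversed direction. If progression leads to removal, month-12 pairs could be lost unequally by arm, with progression at 56.5% against 34.0%. That second statement assumes exponential PFS at the plan's medians and is an upper guide to loss through progression. The truth could be anywhere down to no such loss.

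The primary endpoint and sample size are unaffected. Quality of life is a named secondary objective in a 64-man trial with no power claimed for it, so the change is worth making before the data are analysed but does not threaten the main result.

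**What to change.** In Section 14.5:

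- Replace the overall score with two: pain severity (mean of items 3 to 6) and pain interference (mean of items 9A to 9G). Report item 8 separately.
- Replace the paired t-test with a mixed model for repeated measures over all scheduled BPI visits, with arm, visit, arm-by-visit and baseline score. Report the between-arm difference at month 12 with its confidence interval.
- Report the number of forms received by arm and visit, and by progression status.

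Align the quality-of-life wording in Section 3.3 with the synopsis and Section 14.1.2. Reconcile Sections 6.11 and 6.15 with Sections 6.10 and 14.2 on whether BPI collection continues after progression.

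The cost is two reported scores in place of one and a little more analysis work. It needs no new instrument or visit. The scoring and model are changes to the statistical section only. The statement on collection after progression is a protocol clarification and, if sites now stop collecting at progression, a change in data collection.

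The model uses men with partial data and is valid if missingness depends on observed scores and arm. It does not remove bias if men leave because of pain that no form recorded, which is why the collection rule matters as well.
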